### **10.3.5 Model evaluation**

Model evaluation will include graphical analysis of goodness of fit (GOF) plots, relative standard errors (RSEs), visual predictive checks (VPCs), and possibly other simulation-based diagnostics. Stratifications will be used when appropriate to ensure that the models perform adequately across important subgroups of the data.

### **10.3.6 Model discrimination**

The discrimination between models will mainly be made based on the inspection of graphical diagnostics and changes in the objective function value (OFV) and Akaike information criterion (AIC). The differences in OFVs are nominally  $\chi^2$  distributed and a difference of -3.64 corresponding to approximately a p-value of  $< 0.05$  for one degree of freedom, provided that the models are hierarchical. Preferably this should also demonstrate improvements in the graphical diagnostics and not lead to a high ( $>1000$ ) conditional number.

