#### **4.3 Sample Size Determination**

This is a proof-of-concept study without hypothesis testing. The planned sample size of 15 participants per treatment group is in keeping with other phase 2 trials of this type and accounts for the possibility of up to 3 dropouts per arm which, based on previous studies of this type conducted at these sites, represents a conservative estimate of the expected drop-out rate. Previous EBA studies indicate that a sample size of 12 participants per arm allowed for the identification of proof-of-concept i.e., change in TTP/ CFU compared to no change in TTP/CFU for all evaluated arms.

Fifteen individuals per treatment arm is a standardized sample size for EBA studies and is expected to show any potential effect of the studied drug on EBA. However, a difference in EBA between arms may not be detected if the effect difference is small. The suggested sample size of 15 individuals in conjunction with analysis using mixed effects models has previously been shown to be adequate for the assessment of EBA.

Using 12 participants per arm, a power of 80%, alpha of 0.05, and a between-patient variability in (time-to-positivity) TTP slope of 22% (coefficient of variation), will allow for the detection of EBA-TTP0-14days of 0.0483 hours, corresponding to TTP-EBA0-14days of 11 hours, using a nonlinear mixed effects model (Boeree, M. J., et al, 2015).

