## 10.3.2 Stochastic model (Random Effects)

### 1. Inter-individual variability

During the course of the model development, the Inter-individual (IIV) parameters will be tested on the structural parameters of the EBA models. Inter-individual parameters will be included in an exponential manner to ensure that the individual EBA parameters have a lower bound of zero:

$$P_i = \text{TVP} \cdot e^{\eta}$$

where TVP is the typical (Expected) value of the parameter P,  $P_i$  is the individual value of the parameter and  $\eta$  is a normally distributed random variable with mean 0 and standard deviation  $\sigma$ . Not all parameters need to be associated with IIV.

If the distributions of the  $\eta$ s are markedly non-normal, transformations of  $\eta$ s may be considered. Terms to describe correlations between  $\eta$ s will also be considered if indicated by the data. Initially, IIV should be added to the baseline only. IIV in other parameters should be explored after the treatment effect evaluation.

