## 10.3.4 Covariate model (Mixed Effects)

After confirmation of the structural and stochastic EBA models a covariate analysis will be done. The median of baseline values of the covariate will be used for time-independent covariates. For time-dependent covariates, the actual value of the covariate at the time of the observation will be used (or closest in time to the observation). The inclusion of time-dependent covariates in the covariate analysis will be informed by the exploratory data analysis. For time-varying covariates to be included in a model there must be a clear rational for assuming that the time variation is independent of the drug treatment and not vice versa. Time-varying covariates

for which the causality is unclear may be investigated after the assessment of other covariates or drug effects.

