### **10.3.8 Final model**

A final model should provide a good description of the observed data, not have any important trends in the relevant GOF diagnostics, have a successful termination of the covariance step and preferably have a condition number less than 1000. Should a model be accepted as final without these criteria being met, it will be discussed and justified in the report.

There will be one final model for each of the endpoints.

Based on the final EBA models for TTP and CFU, mean bactericidal activity per treatment arm will be expressed as the daily change in TTP and CFU from day 0 to day 14. If required, periods from 0 to 2 days, 0 to 7 days, 7-14 days, or any other period will be predicted or calculated as well as the 95% Bayesian credibility interval using only the patient data included in the study. Clinical trial simulations ( $n= 1000$ ) will be used to predict mean (95% prediction interval) bactericidal activity for different treatment arms and different characteristics depending on the covariates included in the final models.

Early bactericidal activity data definition table (DDT): A separate data specification table will be created for EBA. The dataset should be in excel csv format. A readme file describing the dataset column names should be created with an example for 1 participant.

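### SAP 10.3.6 misstates the 5% cut-off for the objective function value on one degree of freedom: 3.64 should be 3.84 (small effect)

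*SAP*

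**What the plan says.** SAP 10.3.6 discriminates between models mainly by graphical diagnostics and by changes in OFV and AIC. For hierarchical models on one degree of freedom it gives "a difference of -3.64 corresponding to approximately a p-value of" below 0.05. It prefers that such a gain also improves the graphics and does not bring a condition number above 1000.

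The neighbouring sections set the context:

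- **SAP 10.3.2.** Inter-individual variability (IIV) "parameters will be tested on the structural parameters of the EBA models". The order is: "Initially, IIV should be added to the baseline only. IIV in other parameters should be explored after the treatment effect evaluation". It adds: "Not all parameters need to be associated with IIV".
- **SAP 10.3.4.** "After confirmation of the structural and stochastic EBA models a covariate analysis will be done".
- **SAP 10.3.8.** "Based on the final EBA models for TTP and CFU, mean bactericidal activity per treatment arm will be expressed as the daily change" from day 0 to day 14. On its final-model criteria: "Should a model be accepted as final without these criteria being met, it will be discussed and justified in the report".
- **SAP 4.3.** The detectable-effect statement assumes "a between-patient variability in (time-to-positivity) TTP slope of 22% (coefficient of variation").

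**The concern.** The 3.64 is the only numerical test threshold that the SAP gives for choosing between nested models, and those models produce the primary endpoint. An analyst will apply the printed number, and it does not deliver the level printed beside it.

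The order of model building raises a lesser question. The SAP expects patients to differ in TTP slope, but IIV on the slope is explored only after the treatment effects have been evaluated, and it may be left out. If real slope variability is missing from the final model, the intervals for differences between arms come out slightly too narrow. Protocol 1.2 promises those uncertainties, and Stage 2 is meant to optimise the dosing schedule.

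**Working it through.** **1. The cut-off**

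Inputs from SAP 10.3.6: OFV drop 3.64, one degree of freedom, nested models, stated level p < 0.05.

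- P(chi-square on 1 df > 3.64) = 2 × [1 − Φ(√3.64)] = 2 × [1 − Φ(1.908)] = 0.0564. The plan's figure does not reproduce 0.05.
- The 5% point is 1.960² = 3.84. Back-check: P(chi-square on 1 df > 3.84) = 0.0500.
- No obvious alternative reading gives 3.64. With two degrees of freedom the 5% point is 5.99, and 3.64 gives p = 0.162. With the 50:50 mixture for one variance on its boundary, the 5% point is 2.71.
- When one variance term is added, the boundary p-value is half the usual one: 0.0564 / 2 = 0.028 at 3.64 and 0.0500 / 2 = 0.025 at 3.84. Both are stricter than 5%.

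**2. Slope IIV and the reported contrasts (optional part)**

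From SAP 4.3: slope CV 22%, 12 or 15 participants per arm, and a 0–14 day TTP change of 11 h. **Assumed, because the documents give no values:** residual SD of 20, 30 or 40 h, and larger TTP changes of 42, 70 or 112 h.

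For n patients per arm, slope SD ω, residual SD σ and S = Σ(t − t̄)², the standard error of a two-arm slope contrast is √[2(ω² + σ²/S)/n]. With sampling times 0, 0, 1, …, 14, S = 1015 − 105²/16 = 325.9. Two cases show how much of the variance comes from ω²:

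- 11 h, SD 20 h: mean slope 11/14 = 0.786 h/day; ω² = (0.22 × 0.786)² = 0.030; σ²/S = 400/325.9 = 1.227; share of ω² = 0.030/1.257 = 2%.
- 70 h, SD 30 h: mean slope 5 h/day; ω² = (0.22 × 5)² = 1.21; σ²/S = 900/325.9 = 2.76; share of ω² = 1.21/3.97 = 30%.

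The simulation used five identical arms, lognormal patient slopes, a linear TTP profile, maximum likelihood and 40,000 trials per cell. It gives the false-positive rate of a two-arm slope contrast (Wald test at 3.84) in the final model with all arm terms kept. Ranges run over the three residual SDs and over 12 or 15 per arm.

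| TTP change, 0–14 days | Slope IIV added only if the OFV drop exceeds 3.64 | Slope IIV always in the model |
|---|---|---|
| 11 h (SAP 4.3) | 5.1–5.4% | 4.7–5.0% |
| 42 h (assumed) | 5.8–7.6% | 5.2–6.2% |
| 70 h (assumed) | 6.4–8.0% | 5.8–6.5% |
| 112 h (assumed) | 6.2–7.9% | 6.1–6.8% |

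The largest gap within one cell is 8.0 − 6.4 = 1.6 points (70 h, SD 30 h, 12 per arm), where slope IIV is detected in 35% of trials. At 112 h with SD 20 h it is always detected and the gap is zero. At 11 h with SD 20 h and 15 per arm the gap is 5.3 − 4.9 = 0.4 points. Coverage of the nominal 95% interval is 92.0–94.9% against 93.2–95.3%, and intervals are on average 0–5% narrower when slope IIV is only conditionally included. Replacing the linear profile with one linear in log10(t + 1) changes these rates by about 0.1 points.

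A separate two-arm simulation (normally distributed slopes, cut-off 3.84 for adding slope IIV) gave coverage losses of up to 2.0 points (91.4% against 93.4% at 10 h/day, SD 40 h, 15 per arm). The order of magnitude is the same.

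**The case against.** The strongest defence is that 3.64 is probably a typing error, that the text says approximately, and that graphics and AIC carry much of the decision. All of this limits the damage. None of it makes 3.64 the 5% point.

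Correcting the cut-off also makes slope IIV slightly harder to detect: 34.1% falls to 32.5% at 70 h, SD 30 h, 12 per arm. The effect on the error rate is below 0.1 point, so this is no reason to keep a wrong number.

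On the order of steps, a reader might infer that arm effects are selected in a model without slope IIV, and hence that spurious differences between regimens are kept and reported. The documents do not support that:

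- No section says that arm terms are selected or dropped.
- SAP 10.3.8 requires activity per treatment arm from the final model, so an intermediate fit is not reported.
- SAP 10.3.2 itself plans to explore IIV beyond the baseline.
- SAP 10.3.4 still refers to the assessment of drug effects after the stochastic model is confirmed, although only in passing and in connection with time-varying covariates.
- SAP 10.3 calls itself a summary and leaves fuller model definitions to the EBA statistical report.

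Starting with baseline IIV and adding the rest later is a model-building order, not a mistake.

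The simulation has limits as well. It uses linear or log-time profiles, Wald contrasts and OFV alone, whereas the SAP has logarithmic and exponential TTP functions, Bayesian credibility intervals and visual predictive checks. Differences of one or two points may not carry over exactly.

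**Conclusion.** The cut-off in SAP 10.3.6 is wrong as written and should be 3.84. This rests on the chi-square distribution alone and needs no assumption about the trial. Its size is 5.6% instead of 5.0%, nominally, for a single fixed-effect term, and the other selection criteria dilute it further.

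The slope-IIV point survives only as a clarification worth having. It concerns the width of intervals for arm differences, by at most about 1.6 points of error rate in the five-arm simulation under assumed TTP changes and residual SDs, and about 0.4 points at the SAP's own 11 h. Even with slope IIV always included, the rate reaches 6.8% with these group sizes.

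Neither part shows a fault in the Stage 1 decision. SAP section 9 sets its own 5% level for the tds slope against zero and does not name the OFV rule. The study is also described as one without hypothesis testing, and no formal 5% comparison between arms is declared.

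**What to change.** **Needed:** in SAP 10.3.6, replace -3.64 with -3.84. This changes one number and costs nothing.

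**Optional:** add one sentence to SAP 10.3.2: arm contrasts and their intervals are reported from a final model in which IIV on the slope (EBA rate) parameter has been tested and kept where it can be estimated stably, judged by the covariance step and condition number already used in 10.3.6 and 10.3.8; any omission is justified in the report, as 10.3.8 already requires when its own criteria are not met. The cost is a little more model fitting and, under the assumptions above, intervals about 0–5% wider.

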### **10.3.7 Evaluation of shrinkage**

Shrinkage in Empirical Bayes Estimates (EBEs) of model parameters used for diagnostic purposes will be evaluated. The shrinkage increases from 0 towards 100% as the EBEs becomes less informative, and EBE based graphs and diagnostics are more reliable when shrinkage is small. A shrinkage of  $<20\%$  is generally considered as a low shrinkage. Shrinkage will be taken into account when EBE based graphs and diagnostics are evaluated.

### **10.3.8 Final model**

A final model should provide a good description of the observed data, not have any important trends in the relevant GOF diagnostics, have a successful termination of the covariance step and preferably have a condition number less than 1000. Should a model be accepted as final without these criteria being met, it will be discussed and justified in the report.

There will be one final model for each of the endpoints.

Based on the final EBA models for TTP and CFU, mean bactericidal activity per treatment arm will be expressed as the daily change in TTP and CFU from day 0 to day 14. If required, periods from 0 to 2 days, 0 to 7 days, 7-14 days, or any other period will be predicted or calculated as well as the 95% Bayesian credibility interval using only the patient data included in the study. Clinical trial simulations ( $n= 1000$ ) will be used to predict mean (95% prediction interval) bactericidal activity for different treatment arms and different characteristics depending on the covariates included in the final models.

Early bactericidal activity data definition table (DDT): A separate data specification table will be created for EBA. The dataset should be in excel csv format. A readme file describing the dataset column names should be created with an example for 1 participant.

## 11 Reporting

The Demography, Baseline Characteristics, Safety and Tolerability, and EBA analysis results will be reported. The CSR will incorporate these in one report. The statistical reports are independent and will be reported in parallel. The interim analysis report will be focused on safety and EBA.

### 11.1 Demography and Baseline

The results of the demographic and safety analysis will be reported as per the tables listed below:

| Table Number          | Population       | Table Title  | Shell/ Reference to Shell |
|-----------------------|------------------|--|---------------------------|
| 14.1 Demographic Data |                  |  |                           |
| 14.1.1                | All Participants | Disposition of Participants                                    | S                         |
| 14.1.2                | Safety           | Demographics   | S                         |
| 14.1.3                | Safety           | Medical History  | S                         |
| 14.1.4                | Safety           | Vital Signs at Baseline  | 14.1.2                    |
| 14.1.6.1              | Safety           | Physical Examination at Baseline                               | S                         |
| 14.1.7                | Safety           | Prior Medications  | S                         |
| 14.1.8.1              | Safety           | Clinical Safety Laboratory Tests at Baseline – Haematology     | 14.1.2                    |
| 14.1.8.2              | Safety           | Clinical Safety Laboratory Tests at Baseline – Serum Chemistry | 14.1.2                    |
| 14.1.8.3              | Safety           | Clinical Safety Laboratory Tests at Baseline – Urinalysis      | 14.1.2                    |
| 14.1.9                | Safety           | Mycobacteriological Characteristics at Baseline                | 14.1.2                    |
| 14.1.10               | Safety           | Exposure and Compliance  | 14.1.2                    |
| 14.1.11               | Safety           | Substance Use  | 14.1.2                    |
| 14.1.12               | Safety           | Methemoglobin Assessment                                       | 14.1.2                    |
| 14.1.13               | Safety           | Lung Function Assessment                                       | 14.1.2                    |

RESP30X-EBA: Statistical Analysis Plan22 JUL 2024**11.2 Safety and Tolerability**

The results of the safety and tolerability analysis will be reported as per the tables, listings and figures listed below:

| Listing Number       | Listing Title / Summary   |
|----------------------|---|
| 16.2 Safety Listings |   |
| 16.2.1.1             | Study Completion Status   |
| 16.2.1.2             | Visit Dates (including hospital admission and discharge)                              |
| 16.2.2               | Eligibility and Inclusion and Exclusion Criteria                                      |
| 16.2.3               | Subject Eligibility (including Informed Consent, Initial Diagnosis and Randomization) |
| 16.2.4.1             | Demographic Data  |
| 16.2.4.2             | Medical History   |
| 16.2.4.3             | Urine Drug Screen   |
| 16.2.4.4             | Serum Pregnancy   |
| 16.2.4.5             | Serology (HIV) and CD4 Count  |
| 16.2.4.6             | Prior and Concomitant Medication  |
| 16.2.5               | Study Drug Administration (including compliance)                                      |
| 16.2.6.1             | Adverse Events  |
| 16.2.6.2             | Physical Examination  |
| 16.2.6.3             | Vital Signs   |
| 16.2.6.4             | Chest X-ray   |
| 16.2.7               | Clinical Safety Laboratory Tests  |
| 16.2.8               | Study Stopping and Amendment Criteria (for interim analysis)                          |
| 16.2.9               | Substance Use   |

RESP30X-EBA: Statistical Analysis Plan22 JUL 2024

| Listing Number | Listing Title / Summary  |
|----------------|--------------------------|
| 16.2.10        | Methemoglobin Assessment |
| 16.2.11        | Lung Function Assessment |

| 14.3 Safety Data |            |  |                           |
|------------------|------------|--|---------------------------|
| Table Number     | Population | Table Title  | Shell/ Reference to Shell |
| 14.3.1.1         | Safety     | Summary of Incidence of Treatment Emergent Adverse Events  | S                         |
| 14.3.1.2         | Safety     | Incidence of Treatment Emergent Adverse Events by System Organ Class and Preferred Term  | S                         |
| 14.3.1.3.1       | Safety     | Incidence of IMP Related Treatment Emergent Adverse Events by System Organ Class and Preferred Term  | 14.3.1.2                  |
| 14.3.1.3.2       | Safety     | Incidence of Potentially IMP Related Treatment Emergent Adverse Events by System Organ Class and Preferred Term                                | 14.3.1.2                  |
| 14.3.1.4         | Safety     | Incidence of Fatal Treatment Emergent Adverse Events by System Organ Class and Preferred Term  | 14.3.1.2                  |
| 14.3.1.5         | Safety     | Incidence of Serious Treatment Emergent Adverse Events by System Organ Class and Preferred Term  | 14.3.1.2                  |
| 14.3.1.6         | Safety     | Incidence of Treatment Emergent Adverse Events leading to discontinuation by System Organ Class and Preferred Term                             | 14.3.1.2                  |
| 14.3.1.7.1       | Safety     | Incidence of Treatment Emergent Adverse Events by System Organ Class, Preferred Term and Maximum Severity                                      | S                         |
| 14.3.1.7.2       | Safety     | Incidence of Potentially IMP-related Treatment Emergent Adverse Events by System Organ Class, Preferred Term and Strongest Relationship to IMP | 14.3.1.7.1                |
| 14.3.1.7.3       | Safety     | Incidence of Treatment Emergent Adverse Events by System Organ Class, Preferred Term and Strongest Relationship to IMP                         | 14.3.1.7.1                |
| 14.3.1.7.4       | Safety     | Incidence of Treatment Emergent Adverse Events by System Organ Class, Preferred Term, Maximum Severity and Strongest Relationship to IMP       | S                         |
| 14.3.1.8         | Safety     | Summary of Frequency of Treatment Emergent Adverse Events  | S                         |
| 14.3.2.1.1       | Safety     | Clinical Safety Laboratory Tests – Haematology over time   | S                         |
| 14.3.2.1.2       | Safety     | Clinical Safety Laboratory Tests – Haematology Change from Baseline over time  | S                         |

RESP30X-EBA: Statistical Analysis Plan22 JUL 2024

|            |        |  |            |
|------------|--------|--|------------|
| 14.3.2.1.3 | Safety | Clinical Safety Laboratory Tests – Haematology Assessment over time                    | S          |
| 14.3.2.2.1 | Safety | Clinical Safety Laboratory Tests – Serum Chemistry over time                           | 14.3.2.1.1 |
| 14.3.2.2.2 | Safety | Clinical Safety Laboratory Tests – Serum Chemistry Change from Baseline over time      | 14.3.2.1.2 |
| 14.3.2.2.3 | Safety | Clinical Safety Laboratory Tests – Serum Chemistry Assessment over time                | 14.3.2.1.3 |
| 14.3.2.3   | Safety | Clinical Safety Laboratory Tests – Urinalysis  | 14.3.2.1.1 |
| 14.3.4     | Safety | Physical Examination   | 14.1.6     |
| 14.3.5     | Safety | Vital Signs  | 14.3.2.1   |
| 14.3.6     | Safety | Concomitant Medication   | 14.1.7     |
| 14.3.7     | Safety | Summary of Assessment of Study Stopping and Amendment Criteria. (for interim analysis) | S          |
| 14.3.8     | Safety | Methemoglobin Assessment Over Time   | 14.3.2.1.1 |

| Figures Number | Population | Figure Title  | Shell/ Reference to Shell |
|----------------|------------|---|---------------------------|
| 14.3.1         | Safety     | Summary of Incidence of Treatment Emergent Adverse Events                           | S                         |
| 14.3.2         | Safety     | Clinically Significant Laboratory Tests by Treatment-Over Time                      | S                         |
| 14.3.3         | Safety     | Clinically Significant Laboratory Tests by Treatment-Change from Baseline over Time | S                         |

